**Figure 1. Schematic overview of the study design.**

* t_0 is the moment that the instillate is evacuated from the abdominal cavity (the end of HIPEC)

4. STUDY POPULATION

4.1 Population (base)

Eligible patients for study entry include patients with a diagnosis of peritoneal carcinomatosis as a result of intra-abdominal cancers who are already planned for HIPEC treatment with oxaliplatin as part of routine clinical care. In Radboud University Medical Centre an average number of one patient per week is being treated with cytoreduction and HIPEC with oxaliplatin. Therefore, it is expected that the planned number of patients (n=20) can be recruited from this group of patients.

4.2 Inclusion criteria

In order to be eligible to participate in this study, a subject must meet all of the following criteria:

- 1) Subjects must provide written informed consent prior to performance of study-specific procedures or assessments and must be willing to comply with treatment and follow-up.

Note: Informed consent may be obtained prior to start of the specified screening window.

Note: Procedures conducted as part of the subject's routine clinical management (e.g., blood count, imaging study) and obtained prior to signing of informed consent may be utilized for screening or baseline purposes.

- 2) Age ≥ 18 years
- 3) Confirmed diagnosis of preoperatively identified primary or recurrent peritoneal carcinomatosis (PC) of colorectal origin who are planned for HIPEC treatment with oxaliplatin according to routine clinical care

4.3 Exclusion criteria

Patients who do not achieve a cytoreduction score of CC-0 will be excluded from the study.

4.4 Sample size calculation

The primary objective of the study is to determine the effect of flushing after HIPEC on tissue exposure of total platinum content. Therefore the difference in tumour exposure within the same subject before and after flushing will be studied. A difference of $\geq 25\%$ is considered as clinical relevant. For the sample size calculation we used an intra-patient variability in tumour exposure of 20%. A sample size of 10 patients is required to show a difference of $\geq 25\%$ (90% confidence interval) with a power of 90% and a one-side significance level of 0.05.

This study will serve as an exploratory study for all secondary objectives. Therefore no sample size calculation for these objectives has been performed. To make a good comparison possible between flushing and non-flushing we include 10 patients who will undergo HIPEC without flushing.

5. TREATMENT OF SUBJECTS

5.1 Investigational product/treatment

Cytoreductive surgery combined with HIPEC is performed according to local standard treatment (APPENDIX 1).

5.2 Use of co-intervention

Not applicable.

5.3 Escape medication (if applicable)

Not applicable.

6. INVESTIGATIONAL PRODUCT

Not applicable. Oxaliplatin is the standard primary HIPEC treatment.

7. NON-INVESTIGATIONAL PRODUCT

Cytoreductive surgery combined with HIPEC is performed according to local standard treatment (APPENDIX 1). One and a half hour before the intraperitoneal administration of oxaliplatin, the patient is treated with an intravenous infusion of folic acid in a dose of $20\text{mg}/\text{m}^2$ administered over 30 minutes. One hour prior to the beginning of IPCH the patient is treated with 5-FU in a dose of $400\text{mg}/\text{m}^2$ administered in 60 minutes to augment the effects of hyperthermic intraperitoneal oxaliplatin. According to local protocol HIPEC is performed using an open abdominal cavity procedure with the skin pulled upwards (coliseum technique). The abdominal cavity is filled with 5% dextrose. 2500IU of heparin are added to this solution. After 5-FU is administered and the instillate solution has reached a temperature of $41\text{-}42\text{ }^\circ\text{C}$, oxaliplatin is administered in a dose of $460\text{ mg}/\text{m}^2$. Oxaliplatin is delivered by the pharmacy in a 5% dextrose solution in the exact dose required for the patient in a concentration of 2mg/ml. Duration of IPCH is 30 minutes.

8. METHODS

8.1 Study parameters/endpoints

8.1.1 Main study parameter/endpoint

- The main study endpoint is to show a difference in tissue platinum exposure of $\geq 25\%$ before and after flushing. Tissue platinum exposure is expressed in concentration platinum per milligram tissue (ng/mg).

8.1.2 Secondary study parameters/endpoints

- To explore the difference in total platinum wound exudate concentration between patients with and without flushing after completion of HIPEC
- To explore, quantify and describe the effect of flushing after HIPEC on systemic unbound platinum exposure
- To explore, quantify and describe the effect of platinum concentration in instillate on tissue platinum exposure
- To explore, quantify and describe the effect of the degree of cytoreduction on systemic unbound platinum exposure
- To explore, quantify and describe the effect of platinum concentration in instillate on systemic unbound platinum exposure

8.1.3 Other study parameters (if applicable)

The following parameters are collected at baseline: date of birth, gender, ethnicity, medical history (including gastrointestinal resections if applicable), body height and weight and current medication.

Furthermore patients will be asked about AEs. Laboratory tests for hematology and biochemistry will be performed as part of routine clinical care.

8.2 Randomisation, blinding and treatment allocation

As this is an open label study, blinding procedures are not applicable. A total of 20 patients will be included in the study. The first 10 included patients belong to the *flushing* group and the last 10 included patients belong to the *non-flushing* group.

8.3 Study procedures

After the patient has given written informed consent, each patient will undergo an enrolment medical examination in the 14 days prior to the HIPEC procedure. In table 1 a summary is listed of the parameters that should be collected prior to the HIPEC procedure.

Table 1: summary of study procedures during the study

Procedure	Baseline	Day 1	Day 2	Day 3
Time window	-14d			
Informed consent form	X			
Demographics ^a	X			
Medical history/progress notes	X			
Concomitant medication and herbs	X			
Treatment toxicity/ AEs (CTCAE v4.0)				
Routine laboratory tests ^b	X	X	X	X
Pharmacokinetics ^c		X	X	X
Tissue sampling		X		
Exudate sampling		X	X	X
Electrocardiogram	X	X		

- a. Date of birth, gender, ethnicity, body weight, body height and current smoking status.
- b. Including Karnofsky performance status (see APPENDIX 2).
- c. Oxaliplatin administration at the hospital, blood samples at 10, 20 and 30 minutes after the start of HIPEC and at 1/4, 1/2, 1, 2, 4, 12, 24, 36, 48 and 72 hours after completion of the HIPEC procedure.

The study procedures overview is given in APPENDIX 3. The study procedures overview displays in detail the days and time-points for PK blood sampling, collection of peritoneal fluid samples, resection of peritoneal tissue and collection of wound exudate. Patients have to come to the hospital at screening and the day prior to the day of surgery. After surgery patients stay for approximately one to two days on the intensive care unit. After the study ended the effect of the cytoreduction and HIPEC procedure will be evaluated according to standard treatment care.

8.4 Withdrawal of individual subjects

Subjects can leave the study at any time for any reason if they wish to do so without any consequences. The investigator can decide to withdraw a subject from the study for urgent medical reasons.

8.5 Replacement of individual subjects after withdrawal

Patients who do not achieve a cytoreduction score of CC-0 will be excluded from the study and replaced by another patient. Patients will be replaced if only <50% of the required pharmacokinetic samples can be collected for any reason. A maximum number of 10 patients will be replaced.

8.6 Follow-up of subjects withdrawn from treatment

Patients will be followed up conform standard routine care. Besides standard clinical care, no additional follow-up for study purpose is required.

8.7 Premature termination of the study

Not applicable. Patients are treated according to routine and consolidated clinical car

9. SAFETY REPORTING

9.1 Temporary halt for reasons of subject safety

In accordance to section 10, subsection 4, of the WMO, the sponsor will suspend the study if there is sufficient ground that continuation of the study will jeopardise subject health or safety. The sponsor will notify the accredited METC without undue delay of a temporary halt including the reason for such an action. The study will be suspended pending a further positive decision by the accredited METC. The investigator will take care that all subjects are kept informed.

9.2 AEs, SAEs and SUSARs

9.2.1 Adverse events (AEs)

Adverse events are defined as any undesirable experience occurring to a subject during the study, whether or not considered related to [the investigational product / trial procedure/ the experimental intervention]. All adverse events as consequence of the additional sample collection in this study that are reported spontaneously by the subject or observed by the investigator or his staff will be recorded.

9.2.2 Serious adverse events (SAEs)

A serious adverse event is any untoward medical occurrence or effect that

- results in death;
- is life threatening (at the time of the event);
- requires hospitalisation or prolongation of existing inpatients' hospitalisation;
- results in persistent or significant disability or incapacity;
- is a congenital anomaly or birth defect; or
- any other important medical event that did not result in any of the outcomes listed above due to medical or surgical intervention but could have been based upon appropriate judgement by the investigator.

An elective hospital admission will not be considered as a serious adverse event.

The investigator will report all SAEs as consequence of the additional sample collection in this study to the sponsor without undue delay after obtaining knowledge of the events.

The sponsor will report the SAEs through the web portal *ToetsingOnline* to the accredited METC that approved the protocol, within 7 days of first knowledge for SAEs that result in death or are life threatening followed by a period of maximum of 8 days to complete the initial preliminary report. All other SAEs will be reported within a period of maximum 15 days after the sponsor has first knowledge of the serious adverse events.

9.2.3 Suspected unexpected serious adverse reactions (SUSARs)

Patients who participate in the study will receive standard treatment conform local procedure. All SUSARs will therefore be handled following standard work procedure. The SUSAR will be reported directly to Lareb (the Netherlands Pharmacovigilance Centre) and Lareb will take care of the data input in EudraVigilance.

9.3 Annual safety report

The sponsor will submit, once a year throughout the clinical trial, a safety report to the accredited METC.

9.4 Follow-up of adverse events

All AEs will be followed until they have abated, or until a stable situation has been reached. Depending on the event, follow up may require additional tests or medical procedures as indicated, and/or referral to the general physician or a medical specialist. SAEs will be reported till end of study within the Netherlands, as defined in the protocol.

9.5 [Data Safety Monitoring Board (DSMB) / Safety Committee]

Regarding the nature of this study no data safety monitoring board will be appointed.

10. DATA ANALYSIS

10.1 Bioanalysis

Platinum concentrations in blood, instillate, exudate and tissue samples will be analyzed at the Cancer biology laboratory in Toulouse or in the Bioanalytical Laboratory of the Netherlands Cancer Institute in Amsterdam. The Cancer biology laboratory uses validated flameless atomic absorption spectrophotometry to measure platinum concentrations (30). The Bioanalytical Laboratory of the Netherlands Cancer Institute uses a validated method based on quantification of Pt by inductively coupled plasma mass spectrometry (31-33).

10.2 Statistical analysis

10.2.1 Primary study parameter(s)

The main study endpoint is to show a difference in tumour platinum exposure of $\geq 25\%$ before and after flushing. The tissue platinum exposure before and after flushing will be compared by performing a paired sample t-test.

10.2.2 Secondary study parameter(s)

- To explore the difference in platinum wound exudate concentration between patients with and without flushing after completion of HIPEC: mean wound exudate concentrations will be calculated for both groups (flushing vs. non-flushing). An independent t-test will be performed to explore differences.
- To explore, quantify and describe the effect of flushing after HIPEC on systemic exposure of oxaliplatin: The mean AUCs of unbound platinum will be calculated. AUCs of flushing vs. no flushing will be compared by performing an independent t-test
- To explore, quantify and describe the effect of platinum concentration in instillate on tissue platinum exposure: Regression analysis will be performed to model the relationship
- To explore, quantify and describe the effect of the degree of cytoreduction on systemic unbound platinum exposure: Regression analysis will be performed to model the relationship
- To explore, quantify and describe the effect of platinum concentration in instillate on systemic unbound platinum exposure: Regression analysis will be performed to model the relationship

PK parameters for unbound platinum (AUC_{0-72h} , C_{max} and t_{max}) will be calculated by non-compartmental analysis. After finalizing the study the data will additionally be analyzed by Nonlinear mixed effect modeling to estimate the PK parameters for the population and the individual patients.

Based on the individual concentration-time data, the following PK parameters will be determined (non-compartmental analysis).

AUC_{0-72h} : the area under the unbound platinum concentration-time curve calculated (linear trapezoidal method) until the last measurable platinum concentration.

C_{max} : the maximum unbound platinum drug concentration

t_{max} : the time to reach maximum unbound platinum drug concentration.

Individual and mean unbound platinum concentrations will be presented. Overlay presentations will be given to illustrate intersubject variability. Descriptive statistics will be used to calculate the unbound platinum concentration at each sampling time.

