
Objective

Primary objective:

1. To determine the effect of flushing after HIPEC on tissue platinum exposure

Secondary objectives:

1. To explore the effect of flushing after HIPEC on wound exudate platinum concentration
2. To explore the effect of flushing after HIPEC on systemic exposure of total and unbound platinum

3. To explore the relation between the platinum concentration in instillate on tissue platinum exposure
4. To explore the relation between the platinum concentration in instillate on systemic exposure of total and unbound platinum exposure
5. To explore the effect of the degree of cytoreduction on systemic total and unbound platinum exposure

Study design

Single-centre, prospective, open, pharmacokinetic (PK) cohort study.

Study population

Twenty patients with peritoneal carcinomatosis as a result of intra-abdominal cancers who are already planned for HIPEC treatment with oxaliplatin as part of routine clinical care will be included in the study.

Intervention

The first 10 patients will undergo HIPEC procedure with flushing afterwards (the current practice by Radboudumc), followed by 10 patients who will be treated with HIPEC without flushing afterwards (new Radboudumc protocol that will be implemented in the beginning of 2018). Peritoneal fluid, peritoneal tissue, blood and wound exudate samples will be collected in all patients on prespecified time points during and after the HIPEC procedure.

Main study parameters/endpoints:

The main study parameter is the change in tissue platinum exposure before and after flushing. Tissue platinum exposure is expressed in concentration platinum per milligram tissue (ng/mg).

Nature and extent of the burden and risks associated with participation, benefit and group relatedness

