In order to balance cytotoxic activity and risk of toxicity, which is related to systemic exposure, it is important to study the PK of oxaliplatin during the HIPEC procedure. Based on previous PK work the most efficient dose for administration of oxaliplatin during HIPEC has been defined (8, 9, 14-27). The recommended dose of oxaliplatin is 460 mg/m^2 perfused during 30 minutes at 43°C in dextrose 5% following the open 'coliseum' technique. The open 'coliseum' technique is chosen because previous experimental data suggest higher tissue penetration and a more homogenous distribution compared to the closed technique (28). Some studies suggest the use of a standard volume of instillate of 2 L/m^2 , leading to a fixed concentration of oxaliplatin in the peritoneal cavity (9). In the Radboud University Medical Centre the abdominal cavity of the patient is completely filled with dextrose 5% before oxaliplatin is administered, to ensure contact with the whole peritoneum, for which a volume up to 6 litres may be needed. Because the volume of the abdominal cavity differs largely between patients, there is a great variety of oxaliplatin concentration in the instillate and thereby in the abdominal cavity. Together with the duration of the procedure, oxaliplatin concentration in instillate is an important variable that might influence tumour penetration and systemic absorption (9, 16, 21). In addition to these variables tumour penetration can be influenced by several other pharmacokinetic and non-pharmacokinetic variables, including carrier solution, pressure, tumor nodule size, nodule density, vascularity and interstitial fluid pressure.

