3. STUDY DESIGN

Patients

Eligible patients for study entry include patients with a diagnosis of peritoneal carcinomatosis as a result of intra-abdominal cancers who are already planned for HIPEC treatment with oxaliplatin as part of routine clinical care. To determine the effect of flushing after HIPEC on tissue exposure (primary objective) a group of 10 patients are needed who undergo HIPEC with flushing afterwards. To explore the differences of flushing vs. non-flushing (secondary objectives) 10 more patients are needed who undergo HIPEC without flushing afterwards. Cytoreductive surgery and HIPEC will be performed according to the standard local procedure.

Flushing

Flushing after HIPEC will be performed in the first 10 patients. Flushing will be performed immediately after evacuation of the instillate. In this study the abdominal cavity will be flushed during 5 minutes with 2L/m² of sodium chloride 0.9%.

PCI score

To explore the effect of the degree of cytoreduction on systemic exposure of unbound platinum it is necessary to objectively classify the extensiveness of the peritoneal cancer and thereby the intensity of the surgical intervention. As part of routine work the peritoneal cancer index (PCI) is assessed prior to cytoreduction.

CC-score

To completeness of cytoreduction score (CC-Score), as described by Jacquet et al (29), is used to score the completeness of the surgery. A CC-0 score indicates that no macroscopic peritoneal tumour remains after cytoreduction, a CC-1 score indicates that persisting tumour nodules are < 2.5 mm, a CC-2 score indicates residual tumour nodules between 2.5 mm and 2.5 cm and a CC-3 score indicates tumour nodules > 2.5 cm or a confluence of unresected tumour. All patients who do not achieve a CC-0 score will be excluded.

Peritoneal tissue samples

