Two 5-cm diameter non-tumour peritoneal tissue samples will be taken from all patients that underwent HIPEC with flushing afterwards. The first sample will be taken immediately after the instillate solution is evacuated from the abdominal cavity. The second sample will be taken immediately after flushing. In the group of patients receiving HIPEC without flushing one 5-cm diameter non-tumour peritoneal tissue sample will be taken immediately after the instillate solution is evacuated from the abdominal cavity. Immediately after resection, all tissue samples will be touched to filter paper in order to remove excess surface fluid. The processing of the tissue will be performed according to the method described by Elias et al. The concentration in non-tumour peritoneal bathed tissue is a good reflection of tumour bathed tissue (9).

Peritoneal fluid samples

To determine the decrease in concentration of unbound platinum concentrations in the heated peritoneal instillate three different 5ml fluid samples will be collected at the following time points: 5 minutes after the start of the HIPEC procedure, 15 minutes after the start of the procedure and at the end of the HIPEC procedure. Based on the measurements in these samples it is possible to follow the decrease of unbound platinum concentrations in the heated peritoneal instillate. An additional 5ml fluid sample will be taken from the sodium chloride 0.9% flush solution at the end of flushing, to determine unbound platinum concentration in the flushing fluid.

Blood samples

A total of thirteen 10ml heparinised blood samples will be collected from each patient. Each sample will be centrifuged within 10 minutes after collection for 5 minutes (1,000 g, 4°C) to separate plasma. Unbound platinum will be obtained by centrifuging the plasma fraction through a 30 kDa cut-off ultrafiltrate filter for 15 minutes (1,000 g, 20°C). Unbound platinum from plasma is performed as soon as possible after blood collection, to prevent a decrease of Pt levels due to progressive *ex vivo* binding of Pt to plasma proteins and erythrocytes. The unbound platinum will be stored at -20°C until analysis. The first three blood samples will be taken at 10, 20 and 30 minutes after the start of HIPEC. The other ten samples will be taken at $\frac{1}{4}$, $\frac{1}{2}$, 1, 2, 4, 12, 24, 36, 48 and 72 hours after completion of the HIPEC procedure.

[figure not shown]

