APPENDIX 3: Study procedures overview

Procedure	Flushing group				
	Screening	Time relative to the day of surgery			
	Day -14 until day 0	Day 0	Day 1	Day 2	Day 3
Written informed consent	X				
Inclusion/exclusion criteria	X				
Anamnesis/medical history	X				
Demography	X				
Concomitant Medications	X				
Laboratory clinical chemistry	X				
Cytoreduction and HIPEC with flushing afterwards ¹		X			
Blood PK sampling ²		X	X	X	X
Peritoneal PK sampling ³		X			
Tissue collection ⁴		X			
Wound exudates sampling ⁵		X	X	X	X

¹ flushing is performed with 2L/m² of sodium chloride 0.9% during 5 minutes

² blood samples (timepoints relative to the start of HIPEC): 10min, 20min, 30min, 45min, 1h, 1½ h, 2h, 4h, 12h, 24h, 36h, 48h, 72h.

³ peritoneal samples (timepoints relative to the start of HIPEC): oxaliplatin solution: 5min, 15min, 30min; flushing solution: 45min.

⁴ tissue samples of peritoneum: pre- and post-flushing

⁵ wound exudate samples will be taken each time a drain bottle is changes. Sampling continues until the drain is removed or until day 3 post-HIPEC has been reached.

Procedure	Non-flushing group				
	Screening	Time relative to the day of surgery			
	Day -14 until day 0	Day 0	Day 1	Day 2	Day 3
Written informed consent	X				
Inclusion/exclusion criteria	X				
Anamnesis/medical history	X				
Demography	X				
Concomitant Medications	X				
Laboratory clinical chemistry	X				
Cytoreduction and HIPEC without flushing afterwards ¹		X			
Blood PK sampling ²		X	X	X	X
Peritoneal PK sampling ³		X			
Tissue collection ⁴		X			
Wound exudates sampling ⁵		X	X	X	X

¹ no additional flushing is performed

² blood samples (timepoints relative to the start of HIPEC): 10min, 20min, 30min, 45min, 1h, 1½ h, 2h, 4h, 12h, 24h, 36h, 48h, 72h.

³ peritoneal samples (timepoints relative to the start of HIPEC): oxaliplatin solution: 5min, 15min, 30min

⁴ tissue sample of peritoneum after evacuation of oxaliplatin-solution

⁵ wound exudate samples will be taken each time a drain bottle is changes. Sampling continues until the drain is removed or until day 3 post-HIPEC has been reached.

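### The flushing versus no-flushing AUC comparison is an unadjusted t-test on two consecutive groups of 10, although pre-flush values that could sharpen it are already collected

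*Protocol*

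**What the plan says.** Section 10.2.2 fixes the test for the systemic-exposure objective: "AUCs of flushing vs. no flushing will be compared by performing an independent t-test". No covariate is named. The outcome is unbound platinum AUC0-72h by the linear trapezoidal rule.

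Allocation is by order of entry. The Summary says "The first 10 patients will undergo HIPEC procedure with flushing afterwards", followed by 10 without flushing, and section 8.2 confirms that the last 10 included form the non-flushing group.

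On timing, section 3 says "Flushing will be performed immediately after evacuation of the instillate" and, for plasma, "The first three blood samples will be taken at 10, 20 and 30 minutes after the start of HIPEC". Appendix 3 lists, for both groups, "peritoneal samples (timepoints relative to the start of HIPEC): oxaliplatin solution: 5min, 15min, 30min". Section 7 puts the perfusion at 30 minutes.

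On prognostic value, section 1 says "there is a great variety of oxaliplatin concentration in the instillate and thereby in the abdominal cavity" and that "oxaliplatin concentration in instillate is an important variable that might influence tumour penetration and systemic absorption".

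On status, section 4.4 says "This study will serve as an exploratory study for all secondary objectives", with no sample size calculated for them.

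**The concern.** Nothing in the design balances pre-flush exposure between the first 10 and the last 10 patients. The t-test leaves all between-patient variation in its error term, including any part that the early plasma and instillate values would explain. Flushing cannot affect those values, because they are taken before it happens, so they are legitimate covariates.

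Section 10.2.2 does plan a regression of systemic exposure on instillate concentration, and mixed-effects PK modelling. The regression is a separate analysis, and the modelling is described only as estimating PK parameters. Neither is stated to estimate an adjusted flushing effect.

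The result has a use. The Summary's rationale would recommend flushing if tissue exposure is unaffected and systemic exposure, exudate platinum or both are reduced. With 10 per group and a wide interval, a true absence of reduction is hard to tell from a reduction that was missed. The documents do not show that the groups will differ in pre-flush values; the issue is lost precision and openness to imbalance.

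**Working it through.** **The plan's own figures.** None is given for the AUC comparison. The only calculated figure is n = 10 for the paired primary comparison (section 4.4: 25% difference, 20% intra-patient variability, 90% power, one-sided 0.05). It reproduces on the log scale: σ = √ln(1 + 0.20²) = 0.198; SD of the paired difference = √2 × 0.198 = 0.280; effect = |ln 0.75| = 0.288; power at n = 10 is 91.1%. That calculation does not cover the between-group comparison.

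**Are the covariates pre-flush?** Plasma is sampled at 10, 20 and 30 minutes from the start of HIPEC, perfusion lasts 30 minutes, and the flush follows evacuation. Instillate is sampled at 5 and 15 minutes and at the end of perfusion (section 3, Appendix 3). The Summary instead gives 10, 20 and 30 minutes for instillate. Under either version the samples precede the flush.

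**Inputs for the AUC comparison.** From the protocol: 10 per group. Assumed: log-normal AUC; CV 30%, 40% or 50%; true ratio 0.75, borrowed from the tissue threshold in section 4.4; two-sided 0.05; correlation ρ between log AUC and the covariate from 0 to 0.8.

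**Formulas.**
- SD of log AUC: s = √ln(1 + CV²) = 0.294, 0.385, 0.472.
- t-test, 18 df: noncentrality = 0.288/s × √(10/2) = 2.19, 1.67, 1.36.
- ANCOVA with one covariate, 17 df: residual variance is multiplied by (1 − ρ²), and the variance of the group difference by a further 1 + 1/16 on average for covariate imbalance.

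**Power.** The t-test column is exact (noncentral t). The ANCOVA columns are from simulation, 40,000 trials per cell, and agree with the noncentral t to within half a percentage point.

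| CV | t-test | ρ = 0 | ρ = 0.25 | ρ = 0.5 | ρ = 0.7 | ρ = 0.8 |
|---|---|---|---|---|---|---|
| 30% | 54.5% | 52.0% | 53.9% | 64.3% | 80.2% | 91.6% |
| 40% | 35.3% | 33.4% | 35.4% | 42.5% | 57.2% | 72.5% |
| 50% | 25.2% | 24.1% | 25.0% | 30.4% | 41.6% | 54.7% |

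Simulated type I error is about 5% for both methods.

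**Median 95% CI for the AUC ratio (estimate times/divided by).**

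| CV | t-test | ρ = 0.5 | ρ = 0.7 | ρ = 0.8 |
|---|---|---|---|---|
| 30% | 1.31 | 1.27 | 1.22 | 1.18 |
| 40% | 1.43 | 1.37 | 1.30 | 1.25 |

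**In patients.** Equivalent unadjusted group size is 10/[(1 − ρ²) × 17/16]: 12.5 at ρ = 0.5, 18.5 at 0.7, 26.1 at 0.8. Break-even is where (1 − ρ²) × 17/16 is about 1, so ρ is about 0.25.

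**Chance imbalance.** The SE of the group difference in mean log covariate is s × √(2/10) = 0.131 at CV 30% and 0.172 at CV 40%. One SE is therefore a 14% difference at CV 30% (exp 0.131 = 1.14). With equal CVs it carries over to the unadjusted AUC ratio as exp(ρ × SE): 1.07, 1.10 and 1.11 at ρ = 0.5, 0.7 and 0.8 for CV 30%; 1.09, 1.13 and 1.15 for CV 40%. A carry-over as large as a ratio of 0.75 or its inverse has probability 0.001%, 0.17% and 0.62% (CV 30%), or 0.08%, 1.7% and 3.7% (CV 40%).

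**The case against.** The best defence is that nothing here is wrong: an unadjusted t-test is a standard, valid analysis for a comparison declared exploratory and never sized. That stands, and it limits the point to efficiency. The protocol does name the test, though, so the choice has not simply been left to a later document.

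The gain also rests entirely on an unknown correlation. At ρ = 0.3 power is about 56% against 54.5% (CV 30%), which is almost nothing. The plasma covariate covers 30 minutes of a 72-hour AUC, and section 1 says only that instillate concentration might matter. This stands as a caution. A positive correlation is still plausible, because AUC0-72h contains the first 30 minutes and the protocol itself singles out instillate concentration.

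Even adjusted, a null result may stay inconclusive: at CV 40% and ρ = 0.5, power rises only from 35% to 42%. This is true. Chance imbalance is likewise already reflected in the t-test's standard error, so it is not a separate bias, and calendar-time confounding survives adjustment.

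Missing covariates could cancel the gain. Section 8.5 replaces patients only when fewer than half of the PK samples are obtained. If two patients per group lacked the covariate, complete-case ANCOVA at ρ = 0.5 and CV 30% has about 52% power, below the t-test on all 20. That is a hypothetical loss of samples taken during surgery, but it is a good reason to retain the unadjusted analysis.

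Finally, the recommendation in the Summary first requires no effect on tissue, and systemic exposure is only one of two alternative grounds. This reduces the consequence without removing it.

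**Conclusion.** The point holds as an improvement that should be made, with medium confidence. The planned AUC comparison is valid but leaves unused pre-flush information that every patient is scheduled to provide.

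At correlations of 0.5 to 0.8 and an assumed ratio of 0.75, adjustment adds about 10 to 37 points of power at CV 30%, 7 to 37 at CV 40% and 5 to 30 at CV 50%. At a correlation near 0.25 it adds nothing, and at zero it costs 1 to 3 points. The CV, the effect and the correlation are all assumptions, since the documents give none of them. The primary endpoint and its sample size are not affected.

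**What to change.** In section 10.2.2, replace the AUC t-test with an ANCOVA of log AUC0-72h on group and one prespecified pre-flush covariate. Candidates are log unbound platinum plasma AUC0-30min or log instillate concentration. Name one in advance; if it is instillate concentration, first reconcile the sampling times in the Summary with section 3 and Appendix 3. Report the adjusted geometric mean ratio with its confidence interval, and keep the unadjusted t-test on all patients as a sensitivity analysis. AUC from evacuation to 72 hours can be an optional supportive analysis. State that the adjustment does not remove other calendar-time differences between the first 10 and last 10 patients.

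The cost is one model line and no new samples. One residual degree of freedom is spent (18 to 17), with a loss of 1 to 3 power points if the covariate proves unrelated to AUC. The estimate becomes a ratio of geometric means instead of a difference in mean AUCs.
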